2.3.2 Benefit Assessment

This study will enroll subjects with solid tumors, including glioma, chondrosarcoma, or cholangiocarcinoma. This study provides an opportunity for subjects with glioma, chondrosarcoma, or cholangiocarcinoma to participate in a trial of HMPL-306, a novel agent that targets a mutation that is common among these tumors.

2.3.3 Overall Benefit/Risk Conclusion

At present, there are no IDH1 and/or IDH2 inhibitors approved for treatment of the types of cancers being studied in this clinical trial.

HMPL-306 is a dual inhibitor of IDH1 and IDH2, which, in preclinical studies, has demonstrated similar efficacy to single-target IDH inhibitors (ivosidenib), and may have similar benefit to other IDH1 and/or IDH2 inhibitors in the same class.

Preclinical studies, including toxicology studies, indicate that HMPL-306 is well tolerated.

Taking into account the measures taken to minimize risk to participants in this study, the potential risks identified in association with HMPL-306 are justified by the anticipated benefits that may be afforded to participants with solid tumors with IDH mutations as defined in Section 5.2.

3 OBJECTIVES AND ENDPOINTS

The objectives and corresponding endpoints are summarized in [Table 4](#).

Table 4 Objectives and Corresponding Endpoints

Tier	Objectives	Endpoints
Primary	Part 1 – Dose Escalation: To evaluate the safety and tolerability of HMPL-306, thereby determining the RP2D and/or the MTD of HMPL-306 in subjects with locally advanced or metastatic solid tumors with IDH mutations	MTD and/or RP2D Safety including DLTs, TEAEs, SAEs, ECGs, and clinical laboratory abnormalities
	Part 2 – Dose Expansion: To characterize the safety and tolerability of HMPL-306 in subjects with locally advanced or metastatic solid tumors with IDH mutation	Safety including TEAEs, SAEs, ECGs, and clinical laboratory abnormalities
	Part 2 – Cohort C-1 Only: To determine the 2-HG concentration in surgically resected tumors following pre-surgical treatment with HMPL-306 when compared to untreated tumors	Observed plasma and tumor concentrations of 2-HG
Secondary	Part 1 and Part 2: To assess the preliminary antitumor activity of HMPL-306 in subjects with locally advanced or metastatic solid tumors with IDH mutations	ORR, DCR, DoR, TTR, and PFS
	Part 1 and Part 2: To assess the PK of HMPL-306 in subjects with locally advanced or metastatic solid tumors with IDH mutation	Observed plasma concentrations and PK parameters of HMPL-306
	Part 1 and Part 2: To assess the PD of HMPL-306 in subjects with locally advanced or metastatic solid tumors with IDH mutation	Observed plasma concentrations of 2-HG
	Part 2 – Cohort C-1 Only: To characterize the safety and tolerability of HMPL-306 in subjects with locally advanced or metastatic solid tumors with IDH mutations	Safety including, TEAEs, SAEs, deaths, ECGs, and clinical laboratory abnormalities

Table 4 Objectives and Corresponding Endpoints

Tier	Objectives	Endpoints
Exploratory	Part 1 and Part 2: To explore the relationship between HMPL-306 PK exposure and 2-HG levels and percent inhibition	Changes from baseline in tumor markers, correlation with drug exposure, and association with efficacy and safety parameters
	Part 1 and Part 2: To explore the influence of gene abnormalities other than IDH mutations on safety, efficacy, PD, and PK	
	Part 1 and Part 2: To assess the potential predictive biomarkers or response or progression through collection of serial ctDNA collection	
	Part 2: To explore the relationship between the changes in the frequency of genetic mutation, efficacy, PK, PD, and safety after HMPL-306 treatment in tumor and plasma	
	Part 2 – To assess the OS in subjects enrolled to expansion Cohorts A, B, and D.	OS

2-HG = 2-hydroxyglutaric acid; ctDNA = circulating tumor DNA; DCR = disease control rate; DLT = dose-limiting toxicity; DoR = duration of response; ECG = electrocardiogram; IDH = isocitrate dehydrogenase; MTD = maximum tolerated dose; ORR = objective response rate; OS = overall survival; PD = pharmacodynamics; PFS = progression-free survival; PK = pharmacokinetics; RP2D = recommended phase 2 dose; SAE = serious adverse event; TEAE = treatment emergent adverse event; TTR = time to response.

4 STUDY PLAN

4.1 Study Design

This is a phase 1, open-label, multicenter study to evaluate the safety and tolerability of HMPL-306 administered orally (PO) in treatment of subjects with locally advanced or metastatic solid tumors with IDH mutation.

The study consists of 2 parts: Part 1 (dose escalation) and Part 2 (dose expansion).

4.1.1 Part 1 (Dose Escalation)

The first part of the study is dose escalation where cohorts of subjects will receive ascending oral doses of HMPL-306 to determine maximum tolerated dose (MTD) and/or the recommended phase 2 dose (RP2D). The modified toxicity probability interval-2 (mTPI-2) (Yang 2015) design will be utilized for dose escalation until determination of MTD/RP2D. The mTPI-2 method uses a Bayesian framework and a hierarchical model to compute the dose escalation based on the interval between the toxicity rate of each dose level and target probability (Guo 2017). This study is designed targeting a dose-limiting toxicity (DLT) rate of 25% with an equivalence interval of 20% to 30%.

Like the 3+3 design, the mTPI-2 method incorporates pre-specified escalation rules that can be presented in a table (Table 6). As shown in Table 6, the number of subjects dosed at a given dose level is shown in the columns, while the rows indicate the number of DLTs experienced. The escalation/de-escalation rules from the table will be used for each dose level evaluated; the subject numbers and DLTs do not carry over from cohort to cohort. As an example, within a cohort:

- If none of the 3 subjects experience a DLT → escalate the dose (“E” at column 3 row 0) to the next dose level cohort
- If 1 out of 4 subjects experience a DLT → stay at the same dose level (“S” in column 4 row 1)
- If 2 out of 3 subjects experience a DLT → de-escalate to a lower dose level (“D” at column 3 row 2)
- If 3 out of 3 subjects experience a DLT → the dose is determined to be unacceptably toxic and will not be used again, de-escalate to a lower dose level (“DU” at column 3 row 3)

The following rules apply during dose escalation:

- The initial dose will be 100 mg PO, once a day (QD)
- Although in the mTPI-2 method the cohort size is not fixed, at least 3 subjects will be enrolled at each dose level. When all subjects at a dose level complete DLT assessment, the study will escalate to the next dose level and another 3 subjects will be recruited in the order of dose escalation plan until RP2D or MTD Table 6. A minimum of 3 subjects will be enrolled in each cohort.
- The sample size of a dose cohort that has already passed the preliminary DLT assessment (1 to 3 subjects) and has shown efficacy can be extended to 12 cases in order to further evaluate the safety and efficacy signals of this dose
- The study stage will prematurely end when any of the following conditions are met:

- Excessive toxicity is present in the initial dose
- Although no excessive toxicity is present in the first dose level cohort, if the dose returns to the initial dose according to the rules in Table 6 and excessive toxicity is present at the initial dose (for example, 4 or more DLTs are observed in 6 subjects)

Please see Section CCI.

A cycle of study treatment is defined as 28 days of continuous daily dosing, according to the cohort and dose level. At the starting dose, subjects will be administered HMPL-306 at CCI mg PO, QD, and the dose will escalate successively according to the sequence of CCI mg QD, CCI mg QD, CCI mg QD, CCI mg QD, CCI mg QD, CCI mg QD, and CCI mg QD. (see Table 5). The modified Fibonacci design will be used to escalate the dose (see Table 6 for details on the dose escalation decision).

The addition of dose levels 5 to 8 in Protocol Amendment 2 is based on the cumulative safety and preliminary PK and PD data review conducted by the Sponsor and the Safety Review Committee (SRC) members. Following completion of enrollment of dose levels 1 to 4, the PD data reviewed did not demonstrate the desired level of 2-HG inhibition for the Sponsor and the SRC members to declare the RP2D to move to Part 2. Pharmacokinetic data review showed dose proportional increase in PK exposure over the dose range of CCI mg to CCI mg QD. As there were no DLTs or safety concerns noted in dose levels 1 to 4, the Sponsor and SRC members agreed to continue escalation at higher dose levels.

Table 5 Subject Dose Grouping (Dose Escalation Plan)

Dose Level	Dose of HMPL-306 PO, QD ^a with water
1	CCI mg
2	mg
3	mg
4	mg
5	mg
6	mg
7	mg
8	mg

PO = orally; QD = once a day.

Table 6 mTPI-2 Decision Table for Dose Selection

Target toxicity probability (pT)=25%; $\epsilon_1=0.05$; $\epsilon_2=0.05$

	Number of Patients											
	1	2	3	4	5	6	7	8	9	10	11	12
0	E	E	E	E	E	E	E	E	E	E	E	E
1	D	D	D	S	S	E	E	E	E	E	E	E
2		DU*	D	D	D	D	S	S	S	S	E	E
3			DU	DU	DU	D	D	D	D	D	S	S
4				DU	DU	DU	DU	DU	D	D	D	D
5					DU	DU	DU	DU	DU	DU	D	D
6						DU	DU	DU	DU	DU	DU	DU
7							DU	DU	DU	DU	DU	DU
8								DU	DU	DU	DU	DU
9									DU	DU	DU	DU
10										DU	DU	DU
11											DU	DU
12												DU

E=increased to the next higher dose; D=reduced to a previous lower dose; DLT=dose-limiting toxicity; DU=reduced to a previous lower dose and the current dose will not be used again in this trial; MTD=maximum tolerated dose; mTPI-2=modified toxicity probability interval-2; pT=toxicity probability; S=maintaining the same dose.

*If 2 out of 2 subjects have DLTs when treated at the lowest dose level, the Sponsor, based on recommendations from the Safety Review Committee (SRC), can choose to terminate the study or to enroll 1 more subject.

Note: The horizontal axis indicates the number of subjects who are treated at the current dose, and the longitudinal axis is the number of subjects observed with DLTs. ϵ_1 and ϵ_2 are fractions used to define an equivalence interval of the MTD.

Safety Review Committee

Safety monitoring and evaluation of dose escalation will be carried out by the SRC, which is comprised of the Sponsor and investigators. The SRC will determine whether it is safe to continue to the next predefined dose level, stay at the currently assigned dose level, or whether the dose should be de-escalated to a lower dose level and finally determine the RP2D based on the risk-benefit evaluation.

Dose -Limiting Toxicity

DLT is defined as the occurrence of any of the treatment-emergent adverse events (TEAEs) described in Section 8.1.3 during the DLT assessment window, unless the TEAEs are clearly unrelated to the study drug or judged by the investigator as not clinically significant.

DLT Assessment Window:

For all subjects in dose escalation, DLTs will be assessed during the DLT assessment window of 28 days (Cycle 1 Day 1 [C1D1] through C1D28).

DLT-Evaluable Subject:

A subject is DLT evaluable if the following criteria are met:

- Has received at least 75% of the assigned dose of study medication during the DLT assessment window

OR

- Has not completed the DLT assessment period due to a DLT

For decisions on dose escalation, each dose cohort shall present protocol-required numbers of DLT-evaluable subjects. Subjects who are not DLT evaluable in a dose cohort will be replaced to guarantee the protocol-required numbers of DLT-evaluable subjects for dose escalation evaluations.

Subjects who complete the DLT assessment window and are deemed by the investigator to be benefiting from HMPL-306 treatment will be allowed to continue treatment until disease progression, intolerable toxicity, at the investigator's discretion that the subject can no longer benefit from the study treatment, withdrawal of consent, lost to follow-up, the end of study, or death, whichever comes first.

Maximum Tolerated Dose

The MTD determination will be driven by the mTPI-2 method, and as such, the MTD will be any doses with true toxicity probability in the equivalence interval. For this study, the equivalence interval is defined as 20% to 30%.

Recommended Phase 2 Dose

RP2D determination will take the following criteria under consideration:

- Determination of MTD achieved during the dose escalation part
- Assessment of safety, PK, and PD

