6.2.1.2 Withdrawal from Study

All subjects have the right to withdraw from the study at any time. During the treatment period and follow-up period, a subject who withdraws consent to continue participation in the study will not be followed for any reason after consent has been withdrawn. Every effort should be made to obtain information on subjects who discontinue study drug but who do not withdraw consent to continue participation in the study. If a participant withdraws consent for disclosure of future information, the Sponsor may retain and continue to use any data collected before such a withdrawal of consent.

All subjects who withdraw from the study may request destruction of any samples taken and not tested, and the investigator must document this in the site study records.

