8.2 Adverse Event Reporting

8.2.1 Adverse Event Reporting Period

After signing of the pre-screening informed consent, AEs due to the protocol-required intervention will be collected in the pre-screening phase.

After signing of the main study informed consent, all SAEs and AEs regardless of attribution will be collected until 30 days after the last dose of study drug or start of a new treatment of antitumor therapy, whichever is earlier. The relevant AEs will be followed up until they are recovered to the baseline status, already in a stable state as assessed by the investigator, start of new antitumor therapy, loss to follow-up, death, withdrawal of informed consent, the end of study, or it has been confirmed that the AEs are unrelated to the study drug. After this period, the investigators should report only SAEs that are considered to be related to the study drug.

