9.1.3 Analysis Sets

The following analysis sets are defined for the study:

- Safety analysis set: All enrolled subjects who received at least 1 dose of study treatment will be included in the safety analysis population. Safety evaluation will be performed based on the first dose of study treatment received by a subject. This is the primary population for the safety and efficacy analysis endpoint PFS.

- DLT evaluable analysis set: All subjects enrolled in the dose escalation phase of the study who are evaluable for DLT assessment. A subject is DLT evaluable if he/she meets the following criteria:
 - has received at least 75% of the assigned dose of study medication during the DLT assessment window
- OR
- has not completed the DLT assessment period due to a DLT
- Response evaluable analysis set: All subjects who received study treatment and have a baseline tumor assessment and at least 1 postbaseline assessment will be considered evaluable for antitumor efficacy endpoints such as objective response rate (ORR), disease control rate (DCR), time to response (TTR), and duration of response (DoR)
- PK analysis set: All subjects with at least 1 quantifiable plasma concentration of HMPL-306 will be included in the PK analysis population
- PD analysis set: All subjects with at least 1 quantifiable level of 2-HG in the plasma will be included in the PD analysis population

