7. CHANGE FROM THE PROTOCOL

Here is a list of changes in this analysis plan compared with the protocol

- The DLT- evaluable analysis set definition in the protocol is to include all patients enrolled into dose escalation part of the study who (i) either received at least 75% of assigned doses of the HMPL-306 during the DLT assessment window (i.e. Cycle 1 Day 1 [C1D1] through C1D28) or (ii) experienced a DLT in Cycle 1. However, since these criteria have been incorporated in the SRC review, the DLT-evaluable analysis set will be based on the decision from the SRC review.
- Though there is no protocol amendment, it was noted that the study did not proceed to the dose expansion part. That is, no patients were enrolled to the expansion cohorts A (cholangiocarcinoma), B (skeletal chondrosarcoma), C (low-grade glioma), C-1 (perioperative glioma), and D (any other solid tumor harboring an IDH mutation). Hence, the analysis of the study will be conducted only for the dose escalation part.
- DLT-equivalent summary was defined in the protocol, consider that DLT-equivalent event was not well collected in EDC, this summary will not be done.

REFERENCE

Guo W, Wang S-J, Yang S, et al. A Bayesian interval dose-finding design addressing ckham's Razor: mTPI-2. *Contemp Clin Trials*. 2017;58:23-33.

van den Bent M, Wefel J, Schiff D, Taphoorn M, Jaeckle K, Junck L, Armstrong T, et al. Response assessment in neuro-oncology (a report of the RANO group): assessment of outcome in trials of diff use low-grade gliomas. *Lancet Oncol*. 2011;12:583-93.

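### A subject without a DLT is evaluable on 75% of dose alone, so one whose follow-up stops after 21 doses counts as a full non-DLT with the last week of the window unseen

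*Protocol*

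**What the plan says.** Protocol section 4.1.1 states that "DLTs will be assessed during the DLT assessment window of 28 days (Cycle 1 Day 1 [C1D1] through C1D28", and that "A cycle of study treatment is defined as 28 days of continuous daily dosing, according to the cohort and dose level". The window is therefore 28 days with 28 planned doses.

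A subject is DLT-evaluable on either of two grounds:
- "Has received at least 75% of the assigned dose of study medication during the DLT assessment window"
- "Has not completed the DLT assessment period due to a DLT"

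The second ground applies only to subjects who had a DLT, so for everyone else the dose test is the whole test. Section 9.1.3 carries the same wording into the analysis set ("has received at least 75% of the assigned dose of study medication during the DLT assessment window"). Sections 4.1.1 and 6.2.1.3 replace only subjects who are not evaluable.

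Two other rules decide what is seen after a subject leaves. Under section 6.2.1.2, a subject who withdraws consent "will not be followed for any reason after consent has been withdrawn". Under section 8.2.1, AEs are collected "until 30 days after the last dose of study drug or start of a new treatment of antitumor therapy, whichever is earlier"; after that, only SAEs considered related are reported.

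SAP 3.1.3 leaves the DLT-evaluable set to medical review. SAP 7 restates the protocol rule as subjects who "either received at least 75% of assigned doses of the HMPL-306 during the DLT assessment window" or who had a DLT in Cycle 1. It says the Safety Review Committee (SRC) review already incorporates these criteria, and it adds no observation requirement.

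**The concern.** The criterion measures drug intake, while the quantity that enters Table 6 is whether a DLT occurred over 28 days. The two separate when a subject has taken enough drug but ascertainment stops before Day 28. That subject adds one to the denominator and can add nothing to the numerator from the unseen days. If late DLTs are possible at all, the error runs one way: the DLT rate is understated and the decision moves toward escalation.

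Some DLTs also need follow-up to classify. Section 8.1.3 exempts certain Grade 3 events that recover within 3 days, and Grade 3 hypertension that is downgraded within 1 week. An event that starts just before departure cannot be settled either way.

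Cohorts are small. The planned 27 to 36 subjects over 8 dose levels is 27/8 = 3.4 to 36/8 = 4.5 per level, so one partly observed subject is a large share of the evidence at a dose.

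**Working it through.** **Inputs from the documents.** Window of 28 days, daily dosing, 75% threshold, minimum cohort of 3, target DLT rate 25% with interval 20% to 30%, and Table 6 (all protocol section 4.1.1).

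**Assumption.** The documents do not say when DLTs fall within the 28 days, so a range is shown.

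**Step 1: reproduce Table 6.** I used mTPI-2 with a Beta(1,1) prior and sub-intervals of width 0.1 around 0.20–0.30. The decision is taken from the sub-interval with the largest posterior mass per unit length, and DU is assigned when P(p > 0.25 | data) > 0.95. The prior and the 0.95 cut-off are my settings. All 90 of 90 cells match.

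**Step 2: the threshold.** 0.75 × 28 = 21 doses. A subject dosed on Days 1 to 21 who then leaves has 7/28 = 25% of the window unseen.

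**Step 3: what such a subject shows.** Let p be the true 28-day DLT probability and q the probability that a DLT is seen by Day 21.
- Constant hazard: q = 1 − (1 − p)^0.75. At p = 0.30, q = 0.235.
- Uniform timing: q = 0.75p = 0.225.

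**Step 4: chance of escalating on 0/3.** With k such subjects among three, P(0/3) = (1 − p)^(3 − k) × (1 − q)^k. At p = 0.30:

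| DLT timing | q | P(0/3), k = 1 |
|---|---|---|
| None in last week (same as full observation) | 0.300 | 0.343 |
| 10% in last week | 0.270 | 0.49 × 0.730 = 0.358 |
| Constant hazard | 0.235 | 0.49 × 0.765 = 0.375 |
| Uniform | 0.225 | 0.49 × 0.775 = 0.380 |
| Half in last week | 0.150 | 0.49 × 0.850 = 0.4165, shown as 0.416 |

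Under constant hazard with k = 1, the chance moves from 0.422 to 0.453 at p = 0.25 and from 0.216 to 0.245 at p = 0.40.

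**Step 5: decisions that turn on one such subject.** Removing one unseen non-DLT changes these Table 6 cells:
- 1/4 (S) becomes 1/3 (D)
- 1/6 (E) becomes 1/5 (S)
- 2/7 (S) becomes 2/6 (D)

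0/3 (E) becomes 0/2, which still reads E, but the three-subject minimum would then call for a replacement. Had the unseen subject in fact had a DLT, 0/3 (E) would have been 1/3 (D).

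**The case against.** The strongest reply is that the gap is narrow and that people stand in it.

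A reader might infer that anyone who stops after 21 doses has an unseen final week. The documents do not support that. A subject who only stops drug on Day 21 has AEs collected for 30 days after the last dose (8.2.1), an end-of-treatment visit within 7 (±3) days (6.1.19) and a safety visit 30 (±7) days after that (6.1.20). Table 1 schedules hematology and chemistry at both visits. New antitumor therapy does not end all reporting either: related SAEs are still reported, and section 6.2.1.1 asks that subjects who discontinue be encouraged to attend the end-of-treatment visit. The fully unseen case is withdrawal of consent or loss to follow-up.

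Other text also leans toward full observation. Escalation waits until subjects complete DLT assessment (4.1.1). The initial SRC review expects 28 days of safety data from the first three participants (11.1.1). The SRC decides on escalation and can look past a Table 6 reading, and SAP 3.1.3 and 7 leave the set to that review.

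This limits how often the problem arises and makes it less likely to pass unnoticed. It does not close the gap, because none of these texts is an evaluability criterion. The criteria that SAP 7 says the SRC applied are the dose test and the DLT test. A subject the rule calls evaluable is not replaced unless someone departs from the rule.

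A reader might also infer that losing the Day 22 visit hides a third of laboratory-detected DLTs. Nothing in the documents equates the share of visits with the share of events, so that figure is not used.

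**Conclusion.** The concern holds for subjects without a DLT whose ascertainment stops before Day 28 after at least 75% of the dose. For them the written rule can count a partly observed window as a complete one.

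The size is modest: about 3 to 4 percentage points on the chance of 0/3 at a true rate of 30%, with one such subject in three (0.343 to 0.375–0.380). The range runs from no effect to 0.416. These figures rest on assumed DLT timing and on such a subject being present; the documents give neither the timing nor the frequency.

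A reader might go on to infer that escalation decisions in this study were wrong. The documents do not show that: they do not report any subject of this kind. The protocol supplied is Amendment 2 while the SAP is based on Amendment 3, but the SAP's restatement keeps the dose test and adds no observation requirement, so the point appears to carry over.

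**What to change.** In protocol sections 4.1.1 and 9.1.3, define a DLT-evaluable subject as one who either
- (i) had a DLT in the window, whatever dose was received and whether or not the window was completed; or
- (ii) had no DLT, received at least 75% of the assigned dose, and completed safety observation through Cycle 1 Day 28.

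Limb (i) is needed. If the observation requirement were simply added to the dose test, a subject with at least 75% of dose and a DLT on Day 20 who withdrew consent on Day 24 would meet neither ground. An observed DLT would then be discarded. Limb (i) also agrees with SAP 7, which already describes the second ground as a DLT in Cycle 1.

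The SAP says the study did not proceed to expansion and that only Part 1 is analysed, so new protocol wording cannot alter escalation decisions already taken. The useful step now is in SAP 3.1.3: write in the same criterion, list any subject counted as evaluable without a DLT who was not observed to Day 28, and show DLT rates by dose level without those subjects.

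The cost is a few lines of text, one listing and one extra summary. The downside is a slightly smaller denominator or, if enrolment were still open, an occasional replacement subject.

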7.4 Dose Adjustments

7.4.1 Adjustment of Dose within the DLT Assessment Window

In the DLT assessment window, subjects without DLT must not undergo dose reduction of HMPL-306.

- If a DLT occurs, HMPL-306 administration will be suspended and appropriate supportive treatment will be given
- If a DLT returns to Grade 1 or lower within 14 days, HMPL-306 may be resumed at the previous lower dose if the investigator assesses that the subject may still benefit
- If a DLT has not returned to Grade 1 (inclusive) or lower within 14 days, or DLT reoccurs at the lowered dose, HMPL-306 will be terminated

- If the subject has an AE that does not meet the DLT criteria, the subject should continue HMPL-306 according to the original planned dose; for Grades 3 and 4 non-DLT AEs, HMPL-306 can be suspended as necessary as assessed by the investigator

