3.1.3. DLT-Evaluable Analysis Set

The DLT- evaluable analysis set will be determined based on the medical review.

DLT analysis for the Part 1 dose escalation phase will be performed using the DLT evaluable analysis set.

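### A subject who has a DLT, restarts, completes Cycle 1 and receives under 75% of the assigned dose meets neither DLT-evaluable criterion, in conflict with the Table 6 note and SAP section 7

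*Protocol*

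**What the plan says.** Protocol 4.1.1 sets the window: "DLTs will be assessed during the DLT assessment window of 28 days". A subject is evaluable by either of two criteria. The first is "Has received at least 75% of the assigned dose of study medication during the DLT assessment window". The second is "Has not completed the DLT assessment period due to a DLT". Section 9.1.3 repeats both for the analysis set, the second as "has not completed the DLT assessment period due to a DLT". Sections 4.1.1 and 6.2.1.3 require non-evaluable subjects to be replaced.

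Section 7.4.1 suspends drug when a DLT occurs. It then provides: "If a DLT returns to Grade 1 or lower within 14 days, HMPL-306 may be resumed at the previous lower dose", if the investigator judges that the subject may still benefit.

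Two other places describe the count differently. The note under Table 6 defines its axes as subjects treated at the current dose and subjects seen to have DLTs, with no dose condition. SAP section 7 reports the protocol's second criterion as "experienced a DLT in Cycle 1", says the criteria were built into the Safety Review Committee (SRC) review, and bases the set on that review. SAP 3.1.3 says only that the "evaluable analysis set will be determined based on the medical review". SAP 5.2.11.1 runs the DLT analysis on that set.

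**The concern.** The second criterion should ensure that a DLT always counts, however little drug the subject received. As worded it does so only when the DLT prevents completion of the window. Section 7.4.1 gives a route by which a subject has a DLT and still completes the window. Such a subject depends on the 75% criterion, and the hold that the DLT triggered is what puts that criterion at risk.

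DLTs are part of the Part 1 primary endpoint and drive each dose decision. If subjects leave the count because of how their DLT was managed, the error runs one way: the observed DLT rate falls and escalation becomes more likely.

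**Working it through.** **1. The plan's own table.** Table 6 uses a 25% target with 0.05 on each side. An mTPI-2 calculation with a Beta(1,1) prior, sub-intervals of width 0.10 and exclusion when P(rate > 0.25) exceeds 0.95 reproduces all 90 cells. The prior and the 0.95 cut-off are standard choices that the documents do not state.

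**2. When the 75% criterion fails.** Let d be doses taken before the hold, h days held and f the ratio of restart dose to assigned dose.

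Share received = (d + f(28 − d − h))/28, and the threshold is 21/28 = 75%.

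The doses are redacted, so f is an assumption, shown from 0.5 to 1.0. The value f = 1 is the most lenient bound.

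- f = 1, h = 7: 21/28 = 75.0%, just evaluable.
- f = 1, h = 8: 20/28 = 71.4%, fails.
- f = 1, h = 14: 14/28 = 50.0%, fails.
- f = 0.75, h = 7: at most 74.1%; f = 0.5, h = 7: at most 73.2%. Both fail.
- h = 3: fails for 8 of 24 possible DLT timings at f = 0.75, and 16 of 24 at f = 0.5.

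So every hold of 8 to 14 days followed by a restart within Cycle 1 fails, whatever the doses. Shorter holds depend on timing and f.

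**3. When the second criterion fails.** A subject who restarts and reaches C1D28 has completed the window on a plain reading, so this criterion is not met either.

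**4. What happens to the count.** Take three subjects, one with a DLT who followed this path, and a DLT-free replacement where one is enrolled.

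| Reading | Count | Table 6 |
|---|---|---|
| DLT subject is evaluable (SAP section 7 wording), no replacement | 1/3 | D |
| DLT subject replaced but still counted (Table 6 note) | 1/4 | S |
| DLT subject replaced and not counted | 0/3 | E |

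The same data give three different decisions. Likewise 2/6 (D) becomes 1/6 (E) if one DLT is lost.

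**5. Sensitivity.** Let p be the true DLT rate and q the share of DLT subjects lost. The documents give no q, so the values below are assumptions. The rate among counted subjects is p(1 − q)/(1 − pq), and the chance of 0/3 is (1 − that rate)³.

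| p | q = 0 | q = 25% | q = 50% |
|---|---|---|---|
| 25% | 42.2% | 51.2% | 63.0% |
| 40% | 21.6% | 29.6% | 42.2% |

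Example: p = 40%, q = 25% gives 0.30/0.90 = 0.333, and 0.667³ = 29.6%.

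**The case against.** Much of the opposing case stands.

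- **No sentence discards an observed DLT.** The replacement rule fixes how many evaluable subjects a cohort needs. The worked explanation in 4.1.1 and the Table 6 note speak of subjects dosed or treated and of DLTs seen, and section 8.1.3 defines a DLT by its occurrence in the window. A reader might infer that the protocol removes such DLTs from the count. That is one possible reading, and the documents do not state it. Equally, nothing says a replaced subject's DLT is kept, and 4.1.1 ties escalation decisions to the number of evaluable subjects.
- **The gap is conditional.** A subject with a DLT who still receives at least 75% is evaluable, as is anyone whose DLT follows 21 full doses. A DLT that does not recover in 14 days ends treatment and plausibly meets the second criterion. It would be wrong to infer that every subject who restarts is excluded.
- **The second criterion can be read generously**, as covering a subject who could not complete the window at the assigned dose because of the DLT. The words allow that but do not say it.
- **The SAP set is not simply undefined.** Section 7 states both criteria and says the SRC review used them. If it used them in that form, the final set has no gap. But the form differs from the supplied protocol. The SAP is based on Amendment 3, which was not supplied, so whether the protocol text was changed cannot be checked.
- **Other safeguards exist.** Section 8.2.3 requires each DLT to be confirmed to the sponsor within 2 business days, and the SRC decides on escalation.

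**Conclusion.** The point holds for one defined group: subjects who have a DLT, restart under 7.4.1, complete C1D28 and receive less than 75% of the assigned dose. Under the supplied Amendment 2 they meet neither criterion and are to be replaced. That conflicts with the Table 6 note and with SAP section 7.

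The consequence depends on which text governs the count. If the evaluable definition governs, one lost DLT can turn de-escalate into escalate. The direction is certain, but the size is not: the escalation probabilities above show sensitivity to an assumed share of lost DLTs and are not an expected effect.

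A reader might infer that a DLT was in fact lost or that escalation was biased. The documents do not support that. Section 4.1.1 reports no DLTs at levels 1 to 4, so any effect is confined to levels 5 to 8, for which the documents give no DLT results.

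**What to change.** 1. In protocol 4.1.1 and 9.1.3, unless Amendment 3 already does so, reword the second criterion to: *experienced a DLT during the DLT assessment window, regardless of dose received*. This matches SAP section 7 and changes no dosing rule.
2. In SAP 3.1.3, derive the set from the two criteria and list each subject for whom the SRC or medical review decided otherwise, with the reason.
3. Check every replaced or excluded subject at levels 5 to 8 for a DLT in the window. If there is one, show the Table 6 decision with that subject counted.

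The SAP records that expansion did not proceed, so items 2 and 3 matter most now. The cost is one sentence in each of two protocol sections, a short SAP paragraph and one listing. The only downside is that an observed DLT rate may become less favourable.
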